4.3.4. Sensitivity analyses

The sensitivity analyses for the primary endpoint as described in Section 4.2.3 will also be performed for the secondary endpoints.

4.4. Other Endpoints Analyses

4.4.1. Time to first clinically significant exacerbation and Time to first clinically significant exacerbation requiring hospitalisation and/or ED visit

Ot	Other Endpoints Analyses		
En	ndpoint(s)		
•	Time to first clinically significant exacerbation Time to first clinically significant exacerbation requiring hospitalisation and/or ED visit		

bx's proportional hazards model erms in the model: esponse: time to first clinically significant exacerbation or first clinically significant exacerbation requiring popitalization and/or ED visit ategorical: treatment group, exacerbation exacerbation history (variable (2, 3, 4+)), baseline ICS dose nedium, high), geographical region continuous: baseline pre-bronchodilator % predicted FEV1 ne 'exact' method will be used for handling ties. If the analysis will not run using the 'exact' method, then e 'Efron' method for handling ties will be used instead. aplan-Meier survivor functions will be obtained for each treatment group using PROC LIFETEST with a ME statement.
esponse: time to first clinically significant exacerbation or first clinically significant exacerbation requiring ospitalization and/or ED visit ategorical: treatment group, exacerbation exacerbation history (variable (2, 3, 4+)), baseline ICS dose nedium, high), geographical region ontinuous: baseline pre-bronchodilator % predicted FEV1 ne 'exact' method will be used for handling ties. If the analysis will not run using the 'exact' method, then e 'Efron' method for handling ties will be used instead. aplan-Meier survivor functions will be obtained for each treatment group using PROC LIFETEST with a
An appart of the second
nedium, high), geographical region ontinuous : baseline pre-bronchodilator % predicted FEV ₁ ne 'exact' method will be used for handling ties. If the analysis will not run using the 'exact' method, then e 'Efron' method for handling ties will be used instead. aplan-Meier survivor functions will be obtained for each treatment group using PROC LIFETEST with a
he 'exact' method will be used for handling ties. If the analysis will not run using the 'exact' method, then e 'Efron' method for handling ties will be used instead. aplan-Meier survivor functions will be obtained for each treatment group using PROC LIFETEST with a
he 'exact' method will be used for handling ties. If the analysis will not run using the 'exact' method, then e 'Efron' method for handling ties will be used instead. aplan-Meier survivor functions will be obtained for each treatment group using PROC LIFETEST with a
cking & Diagnostics
ne proportional hazards assumption will be examined by obtaining the Kaplan-Meier estimates of the irvival function S(t) over time separately for each treatment group. In addition, the In (-In[S(t)]) plot will be oduced.
esentation
I ratios and the percent reduction in risk for the pairwise treatment comparisons with associated 95% CIs /alues will be presented.
plan-Meier curves will be presented showing the probability of having an event over time for each ent group separately plotted on the same figure.
f missing data and data excluded due to intercurrent events
ticipants that discontinue study intervention due to reasons related to the COVID-19 pandemic, the ed data for the period following this intercurrent event will be excluded from the analysis. Data for this will be assumed MAR (based on all data included in the analysis under the current estimand strategy). ticipants that withdraw from the study, preventing assessment of the endpoint, the data for the period ng withdrawal will be assumed MAR (using data collected under the proposed estimand strategy).

Analytic approach for change from baseline in SGRQ total score and change from baseline in ACQ-5 score at discrete timepoints during the 52-week period has been included in the secondary endpoints analyse, see Section 4.3.2 for details.

4.4.3. SGRQ total score responder status at Week 52 and ACQ-5 score responder status at Week 52

Other Endpoints Analyses	
Endpoint(s)	
 Proportion of responders according to SGRQ total score (responder defined as achieving ≥4-point reduction from baseline) 	n
 Proportion of responders according to ACQ-5 score (responder defined as achieving ≥0.5-point reduction fr baseline) 	om
Model Specification	
Generalized linear mixed model	
Terms in the model:	
Dependent: response (yes/no)	
Categorical : treatment group, exacerbation baseline ICS dose (medium or high), exacerbation history (variable (2, 3, 4+)), geographical region, visit, subject	
Continuous: baseline (SGRQ Total score, or ACQ-5 score), baseline pre-bronchodilator % predicted FEV1	
Interaction: baseline (SGRQ Total score, or ACQ-5 score)*visit, treatment group*visit	
The model will be fit with an unstructured variance-covariance matrix with one single model to include all vis	sits
where the assessment in question is scheduled to be performed.	

- Computation of confidence intervals for the odds ratios is based on the individual Wald tests.
- The analysis of responder based on SGRQ total scores will include data collected at Weeks 4, 12, 26, 40 and 52.
- The analysis of responder based on ACQ-5 score will include data collected at Weeks 2, 4, 8, 12, 16, 20, 24, 26, 28, 32, 36, 40, 44, 48 and 52. In the event the model fails to run due to too many assessment timepoints, timepoints included in the analysis may be reduced by keeping the timepoints of most interest. Suggested order for dropping timepoints is week 44, 20, 36, 16, 32, 8, 48, 24, 28.

Model Checking & Diagnostics

Pearson residuals will be plotted by using PLOTS=PEARSONPANEL option for the model statement in SAS.
 Results Presentation

- Number and percentage of responders and non-responders for each treatment at each visit
- Odds ratio for pairwise comparisons with associated 95 % CIs and p-values

Handling of missing data and data excluded due to intercurrent events

- For participants that discontinue study intervention due to reasons related to the COVID-19 pandemic, the
 observed data for the period following this intercurrent event will be excluded from the analysis. Data for this
 period will be assumed MAR (based on all data included in the analysis under the current estimand strategy).
- For participants that withdraw from the study, preventing assessment of the endpoint, the data for the period following withdrawal will be assumed MAR (using data collected under the proposed estimand strategy).

4.4.4. Change from baseline in pre-bronchodilator FEV₁ and postbronchodilator FEV₁

Analytic approach for change from baseline in pre-bronchodilator FEV_1 at discrete timepoints during the 52-week period has been included in the secondary endpoint analysis of change from baseline in pre-bronchodilator FEV_1 at Week 52, see Section 4.3.2 for details.

Change from baseline in post-bronchodilator FEV_1 at discrete timepoints during the 52week period will be analyzed in the same approach as for change from baseline in prebronchodilator FEV_1 .

4.4.5. PROMIS Fatigue items score

PROMIS Fatigue items score and change from baseline in PROMIS Fatigue items score will be summaried by treatment group and visit.

4.4.6. **SNOT-22** score

The SNOT-22 questionnaire is administered (post randomisation) at Week 26 and 52. The 22 questions of the SNOT-22 are each graded on a 6-point scale ranging from 0 = 'no symptoms' to 5 = 'as bad as things could be'. The scores for each of the questions are summed to derive the total score which ranges from 0 to 110, with higher scores representing worse quality of life.

Oth	her Endpoints Analyses
En	dpoint(s)
•	Change from baseline in SNOT-22 total score at Week 26 and Week 52
Мо	del Specification, Model Checking & Diagnostics
٠	See Model Specification, Model Checking & Diagnostics for secondary endpoints statistical analyses
•	analysis will include data collected at Weeks 26 and 52.
Мо	del Results Presentation
•	See Model Results Presentation for secondary endpoints statistical analyses (figures will not be presented)
•	SNOT-22 score (absolute value and changes from baseline) will also be summarised by treatment group and
	visit.

Other Endpoints Anal	yses

Handling of missing data and data excluded due to intercurrent events

- For participants that discontinue study intervention due to reasons related to the COVID-19 pandemic, the
 observed data for the period following this intercurrent event will be excluded from the analysis. Data for this
 period will be assumed MAR (based on all data included in the analysis under the current estimand strategy).
- For participants that withdraw from the study, preventing assessment of the endpoint, the data for the period following withdrawal will be assumed MAR (using data collected under the proposed estimand strategy).

4.4.7. Patient-rated response to therapy during the 52-week period

This is an overall evaluation of response to treatment, conducted by the participant at Week 12, 26, 40 and 52 using a rating scale. In this rating scale, a seven-point scale score is used with the following definitions:

- 1 = significantly improved
- 2 = moderately improved
- 3 = mildly improved
- 4 = no change
- 5 =mildly worse
- 6 =moderately worse
- 7 = significantly worse

Patients rated response to therapy will be summarised by treatment group and visit.

4.4.8. Clinician-rated response to therapy during the 52-week period

This is an overall evaluation of response to treatment, conducted by the investigator at Week 12, 26, 40 and 52 using a rating scale. In this rating scale, a seven-point scale score is used with the following definitions:

- 1 = significantly improved
- 2 = moderately improved
- 3 = mildly improved
- 4 =no change
- 5 =mildly worse
- 6 =moderately worse
- 7 = significantly worse

Clinician rated response to therapy will be summarised by treatment group and visit.

4.4.9. Patient Global Impression of Asthma Severity/Change (PGI-S, PGI-C)

Patient Global Impression of Asthma Severity (PGI-S): The participant will complete a PGI-S question at the visits: Randomisation and Screening, Day 1, Week 12, 20, 26, 40, 52. This single global question will ask participants to rate their asthma severity on a five-point scale (no symptoms, mild, moderate, severe, very severe). Responses will be captured electronically.

Patient Global Impression of Change (PGI-C) from Baseline of Asthma Severity:

The participant will complete a PGI-C question from baseline of their asthma severity at Week 12, 20, 26, 40 and 52. The single question will ask participants to rate the overall

change in their asthma severity compared with Day 1 (randomisation) prior to start of study intervention. The rating will use a five-point scale (much better, a little better, no change, a little worse, much worse) and responses will be captured electronically.

PGI-S and PGI-C responses will be summarised by treatment group and visit.

4.4.10. ADSD/ANSD

The ADSD/ANSD is a 6-item self-administered patient-reported diary developed by the PRO Consortium's Asthma Working Group (in accordance with the Food and Drug Administration's PRO Guidance) to facilitate comprehensive and reliable assessment of asthma symptoms from a patient's perspective which received qualification from the FDA in March 2019 supporting use in drug development as an exploratory measure.

The ADSD/ANSD is intended for use by adults and adolescents (aged 12 years and older) who are diagnosed with asthma to rate the severity of their symptoms in the three core categories: breathing symptoms (wheezing, shortness of breath), chest symptoms (chest tightness, chest pain) and cough.

The ADSD/ANSD must be completed twice daily by the participant daily during Run-in phase through Week 16, then to be completed for 1 full week during the week preceding each visit thereafter.:

- The morning diary (ADSD) is to be completed upon waking and refers to asthma symptoms during the night-time.
- The evening diary (ANSD) is to be completed before going to bed and refers to asthma symptoms during the day.

Participants are required to rate the six symptoms at their worst during the respective timeframes using an 11-point numeric rating scale (NRS) ranging from 0 ('None') to 10 ('As bad as you can imagine'). Responses will be captured electronically.

4.4.10.1. ADSD/ANSD Change from Baseline

Sec	condary and Other Endpoints Analyses
	dpoint(s)
•	Change from baseline in Asthma Daily Symptom Diary (ADSD) weekly mean score at timepoints during the 52- week period (weekly up to Week 16 and then every visit)
•	Change from baseline in Asthma Nightly Symptom Diary (ANSD) weekly mean score at timepoints during the 52-week period (weekly up to Week 16 and then every visit)
Мо	del Specification, Model Checking & Diagnostics
•	Similar to model specification, model checking and diagnostics detailed in Section 4.3.2 Response variable: weekly mean scores Baseline score is defined in Section 4.1.2 In the event the model fails to run due to too many assessment timepoints, timepoints included in the analysis may be reduced by keeping the timepoints of most interest. Suggested order for dropping timepoints is every other week prior to week 16. If the model still does not converge, then drop week 44, 20, 36, 32, 48, 24, 28.
Мо	del Results Presentation
•	LS means and LS mean change from baseline values for each treatment group will be presented with their associated standard errors as well as 95% CIs. The estimated treatment difference along with corresponding standard error, 95% CI and P-values for each Week will be presented.

• The LS mean treatment differences (and associated 95% CIs) for all weeks will also be presented graphically.

 ADSD and ANSD weekly mean absolute score and changes from baseline will also be summarised by treatment group and visit. Summary will include weekly mean score at all visits (including all weeks prior to week 16).

Handling of missing data and data excluded due to intercurrent events

Same approach as described in Section 4.3.2

Additional Analysis

The same secondary endpoint analyses will be performed using FAS-ADSD/ANSD-modified analysis set

4.4.10.2. Responder Based on ADSD/ANSD

Endpoint(s)

- Proportion of responders according to ADSD weekly mean score (responder defined as achieving ≥1.2 point reduction from baseline)
- Proportion of responders according to ANSD weekly mean score (responder defined as achieving ≥1.5 point reduction from baseline)

Model Specification

Generalized linear mixed model

- Terms in the model: Dependent: response (yes/no) Categorical: treatment group, baseline ICS dose (medium or high), exacerbation history (variable (2, 3, 4+)), geographical region, visit, subject Continuous: baseline weekly mean score (ADSD/ANSD) Interaction: baseline weekly mean score (ADSD/ANSD)*visit, treatment group*visit
 The model will be fit with an unstructured variance-covariance matrix with one single model to include all visits where the assessment in question is scheduled to be performed.
 Computation of confidence intervals for the odds ratios is based on the individual Wald tests.
 The analysis of responder based on SGRQ total scores will include ADSD/ANSD weekly mean score at Weeks 2, 4, 8, 12, 16, 20, 24, 26, 28, 32, 36, 40, 44, 48 and 52.
 In the event the model fails to run due to too many assessment timepoints, timepoints included in the analysis
- In the event the model fails to run due to too many assessment timepoints, timepoints included in the analysis
 may be reduced by keeping the timepoints of most interest. Suggested order for dropping timepoints is every
 other week prior to week 16. If the model still does not converge, then drop week 44, 20, 36, 32, 48, 24, 28.

Model Checking & Diagnostics

Pearson residuals will be plotted by using PLOTS=PEARSONPANEL option for the model statement in SAS.
 Results Presentation

• Number and percentage of responders and non-responders for each treatment at each visit Odds ratio for pairwise comparisons with associated 95 % CIs and p-values

Handling of missing data and data excluded due to intercurrent events

- For participants that discontinue study intervention due to reasons related to the COVID-19 pandemic, the
 observed data for the period following this intercurrent event will be excluded from the analysis. Data for this
 period will be assumed MAR (based on all data included in the analysis under the current estimand strategy).
- For participants that withdraw from the study, preventing assessment of the endpoint, the data for the period following withdrawal will be assumed MAR (using data collected under the proposed estimand strategy).

4.4.11. Mean number of occasions of rescue medication per day

Daily diary data for rescue medication (salbutamol/albuterol) use will be aggregated over 2-week periods, then the mean daily usage, excluding days with missing data, will be calculated for each 2-week period (Weeks 1-2, 3-4,..., 51-52). Data for each 2-week period, and change from baseline for each 2-week period will be summarised by treatment group and visit. For definition of baseline see Section 4.1.2.

4.4.12. Awakenings at night due to asthma symptoms requiring rescue medication use

Awakening at night due to asthma symptoms requiring rescue medication use will be summarised as for rescue medication use, see Section 4.4.11.

4.4.13. Morning peak expiratory flow (PEF)

Morning PEF will be summarised as for rescue medication use, see Section 4.4.11.

The summaries will be for :

- 1. all data included as per FAS population
- 2. excluding data where asthma medication was taken within 6 hours prior to PEF assessment

The mean change from baseline and associated 95% CIs in morning PEF at all timepoints for the treatment groups will also be presented graphically (for all data).

4.4.14. Daily asthma symptom scores

Daily asthma symptom score will be summarised as for rescue medication use, see Section 4.4.11.

4.4.15. Number of days with oral corticosteroids

Total number of days of oral corticosteroids (OCS) use over 52 weeks that are associated with clinically significant exacerbations per subject will be summarised by treatment group. Also, number of clinically significant exacerbations, number of clinically significant exacerbations treated with OCS, and mean number of days using OCS per clinically significant exacerbations treated with OCS will be summarised by treatment group.

Number of subjects on maintenance OCS at screening, total number of days of maintenance OCS use over 52 weeks and mean number of days of maintenance OCS use per subject will also be summarised by treatment group.

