	
discrete timepoints during the 52-week period
 
 • Change from baseline in Asthma Daily Symptom Diary (ADSD)/ Asthma Nightly Symptom Diary (ANSD) weekly mean score at specified timepoints during the 52-week period • Change from baseline in awakenings at night due to asthma symptoms requiring rescue medication use 2-week mean • Change from baseline in morning peak expiratory flow (PEF) 2-week mean • Change from baseline in daily asthma symptom scores 2-week mean • Change from baseline in mean number of occasions of rescue medication use/day 2-week mean • Mean number of days with oral corticosteroids (OCS) usage over 52 weeks • Change from baseline in pre-bronchodilator FEV₁ and post-bronchodilator FEV₁ at discrete timepoints during the 52-week period • Change from baseline in Sino-nasal Outcomes Test-22 (SNOT-22) score at discrete timepoints during the 52-week period

 • To investigate GSK3511294 versus placebo on top of existing asthma therapy on 
 • patient- and clinician-rated response to therapy • patient global impression of asthma severity and its change from baseline 	
 • Patient-rated response to therapy at discrete timepoints during the 52-week period • Clinician-rated response to therapy at discrete timepoints during the 52-week period • Patient global impression of severity (PGI-S) of asthma at discrete timepoints during the 52-week period • Patient global impression of change (PGI-C) from baseline of asthma severity at discrete timepoints during the 52-week period

 • To investigate the PD effects of GSK3511294 	
 • Ratio to baseline in absolute blood eosinophil count at discrete timepoints during the 52-week period

Objectives	Endpoints

 To investigate the PK of GSK3511294 	
 GSK3511294 plasma concentration at discrete timepoints during the 52-week period
Safety	

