6.9. Concomitant Therapy

At pre-screening and/or screening, information on the participant's baseline maintenance asthma therapy will be collected and recorded in the eCRF.

Any medication or vaccine (including over-the-counter or prescription medicines, vitamins, and/or herbal supplements) that the participant is receiving at the time of enrolment or receives during the study must be recorded in the eCRF along with:

- reason for use
- dates of administration including start and end dates
- dosage information including dose and frequency (any dose changes are to be recorded for OCS)

The Medical Monitor should be contacted if there are any questions regarding concomitant or prior therapy.

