8.2.2. Asthma Exacerbations

Clinically significant exacerbations of asthma are defined by:

Worsening of asthma which requires use of systemic CSs¹ and/or hospitalisation and/or Emergency Department (ED) visit.

¹For all participants, IV or oral steroids (e.g., prednisone) for at least 3 days or a single IM CS dose is required. For participants on maintenance systemic CSs, at least double the existing maintenance dose for at least 3 days is required.

Exacerbations separated by less than 7 days will be treated as a continuation of the same exacerbation.

Details of each asthma exacerbation, including medications used to treat exacerbations should be recorded in the eCRF.

Asthma exacerbations should not be recorded as an AE unless they meet the definition of a SAE.

The time period for collection of exacerbation information in the eCRF will be from the start of study intervention until the Exit Visit or Follow-up Visit if applicable.

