2. STATISTICAL HYPOTHESES

The primary study objective is to test for the superiority of GSK3511294 100 mg SC + SoC following two doses (at Week 0 and at Week 26) compared with placebo + SoC, assessed by the annualised rate of clinically significant exacerbations measured over the study intervention period of 52 weeks.

The study will test at a 5% two-sided significance level the null hypothesis that there is no difference in annualised exacerbation rate between GSK3511294 and placebo.

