5.1.1. Primary Endpoint

The assumed true annualised rate of exacerbations in the placebo arm is 1.18. Based on an assumed true treatment difference of a 50% reduction in annualised exacerbation rate between GSK3511294 + SoC and placebo + SoC, a sample size of 375 randomised participants (250 to GSK3511294, 125 to placebo) will provide 99% power for the primary endpoint at a 5% two-sided significance level [PASS, 2020].

The assumptions for the placebo rate and treatment effect are median values from an elicitation exercise which used Phase 3 anti-IL-5/5R historical data (~50% reduction in exacerbations) and expert opinion. The sample size is based also on an assumption of 0.8 for the dispersion parameter which was observed in two mepolizumab studies [Pavord, 2012; Ortega, 2014]. It was assumed that 14% of participant-years data will be missing due to study withdrawal, which is also consistent with mepolizumab studies.

Based on the assumptions above, the minimum observed treatment difference estimated to result in significance at the 5% two-sided significance level is a 27% reduction in exacerbations for GSK3511294 + SoC compared with placebo + SoC (rate ratio of 0.73).

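### SAP 4.4.15 does not deliver the stated endpoint of days on oral corticosteroids over 52 weeks: no total over all courses is planned, and nothing adjusts for time in study

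*SAP*

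**What the plan says.** Protocol section 3 names the endpoint as "Mean number of days with oral corticosteroids (OCS) usage over 52 weeks". SAP 1.1.1 repeats it, and the estimand table in SAP 1.1.2 assigns it a descriptive summary by treatment group. None of these places restricts the reason for taking OCS.

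SAP 4.4.15 then sets out what will be tabulated:

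- "Total number of days of oral corticosteroids (OCS) use over 52 weeks that are associated with clinically significant exacerbations per subject will be summarised" by arm;
- the number of clinically significant exacerbations, the number treated with OCS, and the mean OCS days per OCS-treated exacerbation;
- separately, how many participants were on maintenance OCS at screening, and total and mean maintenance OCS days.

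The exacerbation-linked and maintenance days are not added together, and no count over all courses appears. The section gives no denominator, no annualisation and no rule for participants who leave early. SAP 4.12, which lists changes from the protocol's analyses, covers only the ADSD and ANSD diaries.

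For a steroid course to define an exacerbation without a hospital admission or ED visit, Protocol 8.2.2 says "IV or oral steroids (e.g., prednisone) for at least 3 days or a single IM CS dose is required". On data capture, Protocol 6.9 has all medication recorded with reason and dates, and adds that "any dose changes are to be recorded for OCS". On follow-up, SAP 5.1.1 states: "It was assumed that 14% of participant-years data will be missing due to study withdrawal".

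**The concern.** There are two gaps between the endpoint's name and its planned summary.

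The first is which days count. An asthma course of one or two days with no admission or ED visit does not meet the exacerbation definition and is not maintenance. The same holds for a short course given for another condition; Protocol 6.9.2 bars regular systemic use for non-asthma conditions, which leaves occasional courses possible. Such days are recorded but enter neither count.

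The second is observation time. If totals are averaged as written, a participant who leaves at Week 10 contributes no OCS days for the other 42 weeks, although nobody observed those weeks. Elsewhere the SAP deals with this: a log-time offset for the primary endpoint (4.2.2), exposure-adjusted incidence for adverse events (4.6.2), and daily means that leave out missing days for rescue use (4.4.11). The same problem arises under the endpoint's own estimand. COVID-19-related discontinuation is handled hypothetically, so if later days are dropped from the count with no matching change to a denominator, they are treated as steroid-free.

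At stake is a by-arm table that will be read as steroid burden over a year but is neither complete in the days it counts nor scaled to a year.

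**Working it through.** **Inputs.** From SAP 5.1.1: placebo rate 1.18 per year, rate ratio 0.50 (active rate 0.59), dispersion 0.8, 14% of participant-years missing, 250 active and 125 placebo. SAP 4.11.2.2 sets mean time in study at 0.86 years. The documents give neither OCS days per exacerbation nor withdrawal by arm; both are assumed below, with ranges.

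**Step 1: reproduce the plan's figure.** The plan states no value for OCS days, so the check is on the primary power, to confirm that 14% missing means 0.86 years of mean follow-up. For a Wald test of the log rate ratio:

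Var = (1/(0.86 × 1.18) + 0.8)/125 + (1/(0.86 × 0.59) + 0.8)/250 = 0.0143 + 0.0111 = 0.0254, so SE = 0.159.

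z = 0.693/0.159 - 1.96 = 2.39, giving power 99.2%. SAP 5.1.1 says "375 randomised participants (250 to GSK3511294, 125 to placebo) will provide 99% power". All 12 cells of SAP Table 7 also reproduce within one point.

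**Step 2: equal withdrawal.** A raw total is the yearly days times mean time in study. With even use over time it captures 0.86 of the yearly days, so it is 14% low in both arms.

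- Ratio: (0.59 × 0.86)/(1.18 × 0.86) = 0.50, unchanged.
- Assuming 7 OCS days per exacerbation: 1.18 × 7 = 8.26 against 0.59 × 7 = 4.13 days per year, difference 4.13. Raw: 7.10 against 3.55, difference 3.55.
- At 5 days per exacerbation the difference falls from 2.95 to 2.54; at 14 days, from 8.26 to 7.10. The loss is 14% each time.

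**Step 3: unequal withdrawal.** The overall loss is held at 14%, for example (125 × 20% + 250 × 11%)/375 = 14.0%. Raw ratio = 0.50 × (1 - active loss)/(1 - placebo loss).

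| Placebo loss | Active loss | Raw ratio | Shift |
|---|---|---|---|
| 10% | 16% | 0.467 | -6.7% |
| 14% | 14% | 0.500 | 0% |
| 16% | 13% | 0.518 | +3.6% |
| 18% | 12% | 0.537 | +7.3% |
| 20% | 11% | 0.556 | +11.3% |

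Dividing by time in study returns 0.50 in every row. The splits are illustrations, not bounds.

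**Step 4: uncounted courses.** If the same share of OCS days is uncounted in both arms, the ratio does not move. If 20% were uncounted on placebo and 10% on active (an assumption), it would shift by 0.90/0.80 - 1 = +12.5%; with the shares reversed, by 0.80/0.90 - 1 = -11.1%. The documents give nothing with which to choose between these.

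**The case against.** The best defence is that this is an endpoint in the Other category with a descriptive summary only: no model, no p-value and no place in the testing hierarchy. That stands, and it limits the consequence to how a table is read.

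A second defence is that the endpoint is worded as a mean number of days, whereas the protocol says annualised rate where it wants one, so dividing by time would change the measure. This stands only in part. The wording also says over 52 weeks, and an average of totals from incompletely observed participants is not a 52-week figure either.

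Third, SAP 4.4.15 is not made up solely of raw totals. Mean days per OCS-treated exacerbation does not scale with follow-up, and the primary analysis reports an exacerbation rate adjusted for time. This is correct, but days per treated episode does not measure burden over a year.

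Fourth, SAP section 1 defers data-handling conventions to the Output and Programming Specification, which is not available here and might contain a withdrawal rule. In addition, stopping study drug for reasons unrelated to COVID-19 does not truncate the count, because off-treatment data are kept; only leaving the study does. Both points are fair. Which days count, and whether a total over all courses exists, are nonetheless settled in the SAP.

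Finally, restricting the count to asthma-related use is defensible. Each missed short asthma course is at most two days, and courses for other conditions may say little about the treatment. If that is the intention, the endpoint's name should say so.

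**Conclusion.** The mismatch is real and modest in consequence. The planned summaries leave out some OCS days that the endpoint includes, and nothing scales them to 52 weeks. Given the plan's own 14% loss, use that is even over time and no adjustment in programming, a raw total is about 14% below the 52-week figure. With equal loss by arm the absolute difference shrinks by the same 14%. The ratio is unaffected by equal withdrawal and moves by about -7% to +11% over the assumed splits. The size of the uncounted component is unknown.

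A reader might infer more than this. The documents do not show that steroid sparing will be understated: the shift can go either way or be zero, because no withdrawal by arm is given. They do not show that unlinked courses are a material share. Nor is this the trial's only view of systemic steroid use, since the primary endpoint counts worsening that requires systemic corticosteroids and SAP 4.4.15 reports OCS-treated exacerbations. The primary conclusion is not affected.

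**What to change.** In SAP 4.4.15, keep the existing summaries and add one by arm: total OCS days from all courses divided by total participant-years in study. Specify that:

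- the observation period is the one used in the primary analysis;
- time after COVID-19-related discontinuation is left out of both numerator and denominator;
- exacerbation-linked, maintenance and other days are shown as components, with each calendar day counted once in the total, since a maintenance user's exacerbation days could otherwise appear twice.

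If only exacerbation-linked and maintenance days are intended, rename the endpoint and list the change in SAP 4.12, but still present days per participant-year.

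The cost is SAP wording and one extra table; the dates, reasons and OCS dose changes are already collected under Protocol 6.9. The drawback is that individual rates from very short follow-up are unstable, so the headline should be the pooled figure per arm and not a mean of individual rates.
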